# D. HTLV-1 Specific CTL Analysis

Hypothesis: Nivolumab will enhance anti-ATLL immune responses, including Tax-specific CTL numbers.

Rationale: Nivolumab will enhance anti-ATLL immune responses, as measured by HTLV-1 specific CTL numbers.

Preclinical and Clinical Results: See Section 2.1 for HTLV-1 Immune Responses (2.1.7).

Assay Methodology: Tax-specific CTLs are determined with PBMCs obtained at baseline, Day 1 of Cycle 3, and end of study endpoint. To stimulate IFN- $\gamma^+$  HTLV-1 Tax-specific CD8+ T cells, we use two pools of overlapping 20 mer peptides (offset by 6 amino acids) spanning the full length of the Tax protein. One hundred thousand CD4-depleted PBMCs are incubated at 37°C for 6 h in the presence a range of concentrations  $(0, 0.01, 0.1, 1, 5 \text{ and } 10 \,\mu\text{M})$  of the Tax peptide pools in duplicate wells. IFN- $\gamma$  production by Tax-specific CTLs is quantified by ELISpot. Spot-forming cells (SFCs) were counted using an automated ELISpot reader. For each peptide pool concentration, the frequency of IFN- $\gamma^+$ Tax-specific CTLs is calculated as follows:  $(SFC^{poolA} + SFC^{poolB} - 2 \cdot SFC^{no peptide})/(total number of CD8^+ T cells)$ . Log10[peptide] is then plotted against the number of IFN- $\gamma^+$  Tax-specific CTLs. Using Graphpad Prism software, the following equation was fitted to the data:  $v = (max)/(1 + 10^{((LogEC50-x) + Hillslope)})$ ; where  $x = \log_{10}$  (peptide concentration); y = % CD8+ cells producing IFN- $\gamma$  at a given peptide concentration; Hillslope = gradient of fitted curve; and max = predicted maximum SFC (i.e., where peptide concentration is not a limiting factor in IFN-y production by Ag specific cells). The effective concentration of peptide that induced IFN- $\gamma$  production by half the maximum number of Tax-specific cells (EC50) is estimated using this equation, and CD8+ T cell avidity was defined as the reciprocal of this value ( $1/EC_{50}$ ). Avidity is expressed in units of  $10^6 \text{ M}^{-1}$ .

Investigator's Experience and Competence with the Assay: [name], the Principal Investigator, has unpublished experience in this assay.

Justification for Number of Patients and Specimens: Blood samples will be obtained at baseline, Day 1 of Cycle 3, Day 1 of Cycle 5, and every 12 weeks thereafter, and at the end of study treatment, in order to examine the correlation between viral RNA levels, clinical response, and other correlative studies. Tumor tissue sample is obtained at baseline and off-study time point (if available) to determine viral RNA levels in the tumor.

# 9.4.1.1 Collection of Specimens

The risks of obtaining the blood samples are that of venipuncture and are minimal. No additional tumor tissue will be obtained beyond that initially obtained for clinical purposes, but no longer needed for those purposes.

# **Blood for PBMC**

For each subject:

- Collect five 10mL green-top (sodium heparin) tubes (BD Vacutainer, Catalog no. 366480) OR five 8.5ml yellow-top (acid citrate dextrose or ACD) tubes (BD Vacutainer, Catalog no. 364606) of peripheral blood for the following time point:
  - a) Baseline
- Collect three 10mL green-top (sodium heparin) tubes (BD Vacutainer, Catalog no. 366480) OR three 8.5ml yellow-top (ACD) tubes (BD Vacutainer, Catalog no. 364606) for the following time points:
  - a) Day 1 of Cycle 3
  - b) Day 1 of Cycle 5
  - c) Every 12 weeks (after Day 1 of Cycle 5)
  - d) End of study treatment

# Tumor Tissue

For each subject:

- Obtain tumor tissue sample (block or core) for the following time points:
  - a) Baseline
  - b) End of study treatment (if available)

# 9.4.1.2 Handling of Specimens

# **Blood for PBMC**

- If collected Monday through Thursday, ship tubes on day of collection at room temperature.
- If not shipped on day of collection, isolate and store PBMCs using the PBMC Isolation Procedure (see Table 9.4.1.2 below).
- Label each sample (tube or cryovial) with:

- Study Number NCI9925
- Sample Type **PBMC**
- Subject ID Number
- Collection Date
- Collection Time
- WBC Volume in mL (for cryovials only)

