#### B. Blood Separation

- Fractionate the whole blood by centrifuging at 1500-2000 X g for 10-15 min at room temperature. This will separate the blood into an upper plasma layer, a lower red blood cell (RBC) layer, and a thin interface containing the white blood cells (WBCs) / buffy coat. Fractionate the blood as soon as possible after collection. NOTE: In a typical clinical centrifuge 1500-2000 X g is ~3000-3400 rpm. Check the appropriate settings for your centrifuge using the nomogram in your user's manual.
- 2. Use a disposable, plastic transfer pipet or Pasteur pipet to slowly and carefully aspirate off the plasma (upper layer) down to about 1 mm above the buffy coat. Do not disturb the buffy coat. Discard the plasma into a 250 mL flask containing bleach.
- 3. Gently recover the buffy coat (WBCs) with a fresh disposable pipet, Pasteur pipet, or 1000 ul micropipettor with a sterile tip. Try not to uptake the RBC layer below the buffy coat.
- 4. Place the recovered buffy coat into the WBC labeled cryovial cooled on ice from step 2.
- 5. Screw on the cryovial cap tightly to prevent isopentane from seeping into the vial.
- 6. Visually estimate the volume of WBCs recovered using the volume lines on the cryovial and write the information on the cryovial label. Buffy coat volume is greater in samples with high WBC counts. Usually you can expect  $\leq 0.5$  mL total.
- 7. Proceed to section C, "Freezing Collected Cells".

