#### C. Freezing Collected Cells

- 1. Set Up Freezing Station
  - Do not perform snap freezing with bare hands. Wear gloves at all times and heavy duty gloves when working with liquid nitrogen or cooled isopentane.
  - Use extreme caution when dispensing liquid nitrogen.
  - Fill a small 100 ml metal beaker about 1/4 full with isopentane
  - Fill the Dewar thermo-flask about 1/3 full with liquid nitrogen.
- 2. Freezing Blood Cells in Cryovial
  - 1. Lower the 100 ml metal beaker containing isopentane half-way into the liquid nitrogen for cooling. The liquid nitrogen will boil as the beaker is lowered, when the isopentane is reaching its freezing point the tone of the boiling will increase for 2-3 seconds.

- 2. Lift the beaker out of the liquid nitrogen once more than you see beads of solid isopentane at the bottom of the beaker (about 2 minutes).
- 3. Use long forceps to hold the cryovial down into the cooled isopentane. Hold for at least 1 minute.
- 4. Use the long forceps to take out the cryovial(s).
- 5. Store vial(s) in -80°C freezer.

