# 9.4.1.3 Shipping of Specimens

# **Blood for PBMC**

• On Monday through Thursday, overnight ship tubes on day of collection at room temperature OR batch ship cryovials at the end of the study on dry ice to the [name] Laboratory at the following address:

[name] / [name] Washington University [name] [name] [contact]

• Please notify the [name] Laboratory ([contact]) of any incoming blood specimen shipments by providing notification two days prior to shipment via the 9925 Study Portal. The shipment notification will include upload of the PBMC Shipment Log (see Appendix F). The 9925 Study Portal may be accessed through the following link: http://j.mp/2g4kpUG

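### Blood not shipped on the day it is drawn is stored as snap-frozen buffy coat, which cannot be expected to work in the CTL ELISpot and may not be comparable with fresh PBMCs for viral load

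*Combined protocol and SAP*

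**What the plan says.** Section 9.4.1.2 (Blood for PBMC) gives the main route: "If collected Monday through Thursday, ship tubes on day of collection at room temperature". The fallback is: "If not shipped on day of collection, isolate and store PBMCs using the PBMC Isolation Procedure". Section 9.4.1.3 is worded more loosely. After the same-day instruction it adds, joined by OR, the alternative to "batch ship cryovials at the end of the study on dry ice".

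Table 9.4.1.2 sets out the fallback:

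- Separation is a single spin: "Fractionate the whole blood by centrifuging at 1500-2000 X g for 10-15 min at room temperature".
- The fraction kept is all the white cells: "Gently recover the buffy coat (WBCs) with a fresh disposable pipet".
- Freezing is described by the table itself as snap freezing ("Do not perform snap freezing with bare hands"), and is done in isopentane chilled by liquid nitrogen: "Use long forceps to hold the cryovial down into the cooled isopentane". Storage is at -80°C.

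The table lists no density gradient, freezing medium, cryoprotectant or viability check. The vial is still labeled as PBMC.

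Section 9.4.1 D describes the CTL assay: "One hundred thousand CD4-depleted PBMCs are incubated at 37°C for 6 h", with Tax peptides, read by interferon-gamma ELISpot at baseline, Day 1 of Cycle 3 and end of study. Section 9.4.1 A runs the DNA assay on PBMCs and reports proviral load as a percentage of infected cells. Section 9.4.1 B reports RNA relative to a housekeeping gene. The documents do not say which preparation may be used for which assay, or how a mixture of fresh and frozen samples is to be analyzed.

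**The concern.** Several assays draw on the same blood but need different things from it. ELISpot needs T cells that can still respond. Nucleic acid assays do not need living cells, but a ratio measure needs the same cell mix in its denominator each time. The fallback protects neither requirement.

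Two consequences follow. First, CTL results would be missing for any time point that went down the frozen route. Cryovials are sent only in a batch at study end, so the loss would be discovered when nothing could be collected again. Second, a fresh baseline followed by a frozen follow-up could imitate the fall in proviral load that the protocol hypothesizes, and the reverse order could hide one. Section 13.3 analyzes viral load over time by analysis of variance and uses it as a time-dependent covariate for response duration. Neither model has a term for how the sample was prepared.

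**Working it through.** The plan states no figure on this point, so there is none to reproduce. The check compares each route with what each assay needs, then adds two illustrations under stated assumptions.

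**Which draws are affected.** Fresh shipment runs Monday to Thursday, so every Friday, Saturday or Sunday draw goes to the fallback. Monday to Thursday draws go there only if same-day shipment fails or if a site relies on the looser wording of Section 9.4.1.3.

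**Route against assay.**

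| Assay | What it needs | Fresh tube | Snap-frozen buffy coat |
|---|---|---|---|
| CTL ELISpot (9.4.1 D) | Functioning CD4-depleted PBMCs | Suitable | Not expected to work |
| Proviral DNA (9.4.1 A) | DNA, consistent cell denominator | Suitable | DNA available; denominator may differ |
| RNA (9.4.1 B) | RNA, consistent housekeeping denominator | Suitable | RNA available; denominator may differ |
| FACS (9.4.2) | Blood tested locally | Not dependent on this route | Not dependent on this route |

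**Illustration 1: CTL samples.** Inputs are 20 patients (Section 13.2) and three CTL time points (assay text of Section 9.4.1 D), so 20 × 3 = 60 planned samples. Let s be the share not shipped fresh, which the documents do not give. Expected loss is 60s. If losses are independent, the chance that a patient loses at least one of three is 1 − (1 − s)³.

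| Assumed s | Samples lost, 60s | Patients losing at least one |
|---|---|---|
| 5% | 3 | 1 − 0.95³ = 14% |
| 10% | 6 | 1 − 0.90³ = 27% |
| 20% (one weekday in five) | 12 | 1 − 0.80³ = 49% |
| 40% | 24 | 1 − 0.60³ = 78% |

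Independence is doubtful. Dosing every 14 days tends to keep a patient on one weekday, so losses would cluster: fewer patients affected, but each losing more. In the fully clustered case 20s patients lose all three samples, for example 4 patients at s = 20%.

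**Illustration 2: proviral load.** Let f be the mononuclear share of nucleated cells in the buffy coat. Assume that the other white cells carry no provirus and that the laboratory's fresh preparation excludes them. Then the frozen reading is f × the PBMC reading, lower by a factor of 1/f, and shifted by log2(f) on the scale Section 9.4.1 A uses for normalization.

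| Assumed f | Times lower, 1/f | Apparent fall, 1 − f | log2 shift |
|---|---|---|---|
| 0.8 | 1.25 | 20% | −0.32 |
| 0.6 | 1.67 | 40% | −0.74 |
| 0.4 | 2.5 | 60% | −1.32 |
| 0.2 | 5 | 80% | −2.32 |

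The eligibility limits give one reference point. A patient at both minimums in Section 3.1 has a neutrophil share of 1,500/3,000 = 50%. If the buffy coat mirrors the blood, f is then at most 0.5 and the factor at least 2. Leukemic patients with many circulating malignant lymphocytes would have a higher f, and f would fall if those cells cleared. The distortion can therefore move with response, and one fixed correction would not remove it. The RNA ratio is exposed in the same way, but the documents give nothing from which to size it.

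**The case against.** The best reply is that freezing is a fallback. A reader might infer from the OR in Section 9.4.1.3 that sites may freeze any visit they like, and that a site which did so would lose all its CTL time points. The documents do not support that. Section 9.4.1.2 directs same-day shipment for Monday to Thursday draws, describes no site that freezes routinely, and gives no share of samples frozen. The OR is looser wording that needs aligning.

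The dilution argument also has limits. The protocol does not say how the laboratory prepares PBMCs from fresh tubes; the only method it sets out is the buffy-coat one. A difference in cell population is plausible but not shown. Quoting a 2- to 5-fold effect alone would show only the high-impact end, since Section 2.1.1 describes frequent blood involvement in ATLL and the mononuclear share may be high.

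It is also true that CTL is one assay under a broader objective on immune responses, that local FACS is unaffected, that tumor tissue is studied separately, and that all this sits among the exploratory and ancillary studies of Section 9.4 with descriptive analysis. The route is already largely traceable, because only cryovials carry a white-cell volume and the shipment log counts tubes and cryovials.

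These points limit the scale and the importance. They do not answer the core mismatch: followed as written, the fallback yields vials that cannot be expected to serve the ELISpot, and nothing reserves fresh blood for it.

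**Conclusion.** The concern holds as a minor but real flaw in specimen handling. Any CTL time point that takes the frozen route should be expected to yield no usable ELISpot result, and the problem would surface only after the study. This rests on general laboratory knowledge that T cells snap frozen without cryoprotectant do not function; the documents show the steps but do not state the consequence.

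For proviral load and RNA the issue is comparability, not lost data. Proviral load could read about 1.25 to 5 times lower for an assumed mononuclear share of 80% to 20%, provided that the fresh preparation excludes granulocytes and that the patient's route changes between visits. A reader might conclude that two secondary objectives are undermined. That goes too far: the viral load objective keeps its data, and the immune-response objective keeps FACS, although it would lose its only HTLV-1-specific measure at the affected visits. The number of affected samples is unknown. The primary endpoints and sample size are not touched.

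**What to change.** 1. Require the CTL draws (baseline, Day 1 of Cycle 3, end of treatment) to be taken Monday to Thursday and shipped fresh the same day. Baseline tests already have a two-week window. For the other two, the calendar's one-day tolerance lets a Friday draw move to Thursday or a Sunday draw to Monday; a Saturday draw would need scheduling in advance.
2. State that snap-frozen vials are for DNA and RNA assays only.
3. Align Sections 9.4.1.2 and 9.4.1.3 on when cryovials may be used.
4. In Section 13.3, include preparation route, read from the label and shipment log, as a factor or a sensitivity analysis in the viral load analyses. The blood count with differential is already on the calendar and could inform a further sensitivity analysis on mononuclear share.

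The cost is a few lines of protocol text, one additional analysis term and a small loss of scheduling flexibility at sites. No new test or visit is needed.

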#### Table 9.4.1.2 PBMC Isolation Procedure

#### A. Collection

- 1. Collect blood in specified tube(s).
- 2. Prepare an ice bucket with dry ice. Chill one 2mL cryovial for each tube to collect the white blood cells isolated in the procedure.

#### B. Blood Separation

- Fractionate the whole blood by centrifuging at 1500-2000 X g for 10-15 min at room temperature. This will separate the blood into an upper plasma layer, a lower red blood cell (RBC) layer, and a thin interface containing the white blood cells (WBCs) / buffy coat. Fractionate the blood as soon as possible after collection. NOTE: In a typical clinical centrifuge 1500-2000 X g is ~3000-3400 rpm. Check the appropriate settings for your centrifuge using the nomogram in your user's manual.
- 2. Use a disposable, plastic transfer pipet or Pasteur pipet to slowly and carefully aspirate off the plasma (upper layer) down to about 1 mm above the buffy coat. Do not disturb the buffy coat. Discard the plasma into a 250 mL flask containing bleach.
- 3. Gently recover the buffy coat (WBCs) with a fresh disposable pipet, Pasteur pipet, or 1000 ul micropipettor with a sterile tip. Try not to uptake the RBC layer below the buffy coat.
- 4. Place the recovered buffy coat into the WBC labeled cryovial cooled on ice from step 2.
- 5. Screw on the cryovial cap tightly to prevent isopentane from seeping into the vial.
- 6. Visually estimate the volume of WBCs recovered using the volume lines on the cryovial and write the information on the cryovial label. Buffy coat volume is greater in samples with high WBC counts. Usually you can expect  $\leq 0.5$  mL total.
- 7. Proceed to section C, "Freezing Collected Cells".

#### C. Freezing Collected Cells

- 1. Set Up Freezing Station
  - Do not perform snap freezing with bare hands. Wear gloves at all times and heavy duty gloves when working with liquid nitrogen or cooled isopentane.
  - Use extreme caution when dispensing liquid nitrogen.
  - Fill a small 100 ml metal beaker about 1/4 full with isopentane
  - Fill the Dewar thermo-flask about 1/3 full with liquid nitrogen.
- 2. Freezing Blood Cells in Cryovial
  - 1. Lower the 100 ml metal beaker containing isopentane half-way into the liquid nitrogen for cooling. The liquid nitrogen will boil as the beaker is lowered, when the isopentane is reaching its freezing point the tone of the boiling will increase for 2-3 seconds.

- 2. Lift the beaker out of the liquid nitrogen once more than you see beads of solid isopentane at the bottom of the beaker (about 2 minutes).
- 3. Use long forceps to hold the cryovial down into the cooled isopentane. Hold for at least 1 minute.
- 4. Use the long forceps to take out the cryovial(s).
- 5. Store vial(s) in -80°C freezer.

# Tumor Tissue

- Formalin fixed tumor biopsy prepare as 3x3mm core.
- Fresh tumor tissue (flash frozen in liquid nitrogen within 2 hours of collection) prepare excised tissue or cores measuring at least 10x2x2mm in aggregate.
- Site may opt to send tumor tissue block. Blocks will be handled by the [name] Laboratory per study specifications (not to exhaust the tissue sample) and the remaining tissue will be returned to the site.
- Label each tissue sample with:
  - Study Number NCI9925
  - Subject ID Number
  - Sample Type Block or Core
  - Date of Specimen
  - Corresponding Accession Number

# 9.4.1.3 Shipping of Specimens

# **Blood for PBMC**

• On Monday through Thursday, overnight ship tubes on day of collection at room temperature OR batch ship cryovials at the end of the study on dry ice to the [name] Laboratory at the following address:

[name] / [name] Washington University [name] [name] [contact]

• Please notify the [name] Laboratory ([contact]) of any incoming blood specimen shipments by providing notification two days prior to shipment via the 9925 Study Portal. The shipment notification will include upload of the PBMC Shipment Log (see Appendix F). The 9925 Study Portal may be accessed through the following link: http://j.mp/2g4kpUG

# Tumor Tissue

• On Monday through Thursday, batch ship tissue samples at the end of study at room temperature to the [name] Laboratory at the following address:

[name] / [name] Washington University [name] [name] [contact]

• Please notify the [name] Laboratory ([contact]) of any incoming tissue specimen shipments by providing notification two days prior to shipment via the 9925 Study Portal. The shipment notification will include upload of the Tissue Shipment Log (see Appendix G). The 9925 Study Portal may be accessed through the following link: http://j.mp/2g4kpUG

# 9.4.1.4 Site Performing Correlative Study

Studies will be performed at the [name] Laboratory at Washington University.

# 9.4.2 Immune Cell Numbers - Biomarker of Anti-Tumor Activity

Hypothesis: Nivolumab will enhance anti-ATLL immune responses and will decrease the number of CD3+CD4+CD25+ cells carrying HTLV-1 provirus, while increasing the number of CD3+CD8+ cells without affecting CD56+ or CD19+ cell numbers

Rationale: Nivolumab will enhance anti-ATLL immune responses and decrease infected immune responses and increase anti-ATLL immune effectors, which are likely primarily CD8+ cells

Preclinical and Clinical Results: See Section 2.1 for HTLV-1 Immune Responses (2.1.7).

Assay Methodology: Fluorescence Activated Cell Sorting (FACS) assay to be run at each institution.

# Investigator's Experience and Competence with the Assay: N/A

Justification for Number of Patients and Specimens: Blood samples will be obtained at baseline, Day 1 of Cycle 3, Day 1 of Cycle 5, and every 12 weeks thereafter, and at the end of study treatment, in order to examine the correlation between immune cell numbers, clinical response, and other correlative studies. Tumor tissue sample is obtained at baseline and off-study time point (if available) to determine immune cell numbers in the tumor.

# 9.4.2.1 Collection of Specimens

The risks of obtaining the blood samples are that of venipuncture and are minimal. No additional tumor tissue will be obtained beyond that initially obtained for clinical purposes, but no longer needed for those purposes.

#### **Blood for FACS**

For each subject:

- Collect peripheral blood per standard institutional procedure at the following time points:
  - a) Baseline
  - b) Day 1 of Cycle 3
  - c) Day 1 of Cycle 5
  - d) Every 12 weeks (after Day 1 of Cycle 5)
  - e) End of study treatment

# Tumor Tissue

For each subject:

- Obtain tumor tissue sample per standard institutional procedure at the following time points:
  - a) Baseline (not required if fresh tissue is not available)
  - b) End of study treatment (if available)

9.4.2.2 Handling of Specimens

FACS assay of blood and tumor tissue will be completed per standard institutional procedure. Assay results should include the following: CD3, CD4, CD8, CD19, CD56, and CD25.

9.4.2.3 Shipping of Specimens

N/A

9.4.2.4 Site Performing Correlative Study

FACS assay will be performed at the institution where the patient was enrolled.

# 9.4.3 PD-1, PD-L1, PD-L2 Expression - Biomarker of Anti-Tumor Activity

Hypothesis: Nivolumab responses will be greater in tumors will high levels of PD-L1 or PD-L2 as compared to tumors with low levels of expression of these checkpoint proteins.

Rationale: Nivolumab responses for solid tumors have been shown to correlate with levels of PD-L1 or PD-L2 expression.

Preclinical and Clinical Results: See Section 2.2 on Pharmacodynamics/Biomarkers (2.2.6).

Assay Methodology: IHC assay.

Investigator's Experience and Competence with the Assay: [name], PI of the study, has significant experience with IHC assays.

